1.2. OUTCOME RESEARCH QUESTIONS

For each outcome research question listed above, whether a descriptive or impact design, summarize the inputs (e.g., program components, program supports, implementation features, etc.), target population (e.g., the population for which the effect will be estimated) and the outcomes (e.g., child well-being, father-child engagement, etc.) that will be examined to answer the research question(s). Comparisons for descriptive evaluations may reflect circumstances before the grant, pre-treatment, or pre-determined benchmark from other studies with similar interventions.

Research Question Number	Intervention	Target Population	Comparison	Outcome	Confirmatory or Exploratory?
R1	Ray of Hope curriculum (10 hours) that focuses on domestic violence and related risk factors	Latino fathers: low-income, 18+ years, no open criminal cases (or deferred), children up to 24 years	Parenting attitudes for the treatment group to the control group immediately after completing TCD program.	Healthier parenting attitudes for the Treatment Group that receives enhanced services.	Confirmatory
R2	Ray of Hope curriculum (10 hours) that focuses on domestic violence and related risk factors	Latino fathers: low-income, 18+ years, no open criminal cases (or deferred), children up to 24 years	Partner relationship behaviors for the treatment group to the control group 6 months after TCD enrollment.	Healthier partner relationship behaviors for the Treatment Group that receives enhanced services.	Confirmatory
R3	Ray of Hope curriculum (10 hours) that focuses on domestic violence and related risk factors	Latino fathers: low-income, 18+ years, no open criminal cases (or deferred), children up to 24 years	Parenting behavior for the treatment group to the control group 6 months after TCD enrollment.	Healthier parenting behavior for the Treatment Group that receives enhanced services.	Confirmatory
R4	Ray of Hope curriculum (10 hours) that focuses on	Latino fathers: low-income, 18+ years, no open criminal	Co-parenting behavior for the treatment group to the	Healthier co-parenting behavior for the Treatment	Confirmatory

	domestic violence and related risk factors	cases (or deferred), children up to 24 years	control group 6 months after TCD enrollment.	Group that receives enhanced services.	
--	--	--	--	--	--

* you may add rows by hitting the tab button, or right click and select insert row below

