9.3. RCTS ONLY: POWER ANALYSIS

For each confirmatory outcome, please provide power analyses demonstrating proposed sample sizes will be able to detect expected effect sizes for the outcomes targeted. Refer to previous studies of similar interventions for estimates of the required sample to inform power analyses. Note: If an impact evaluation is not proposed, this issue does not need to be addressed. You may use the table below to report the assumptions used in your power calculations, as well as the resulting minimum detectable impact for your confirmatory outcomes or provide them in the space below.

	Outcome 1	Outcome 2	Outcome 3	Outcome 4
Outcome Name	Healthier Parenting Attitudes	Healthier Partner Relationship Behavior	Healthier Parenting Behavior	Healthier Co-Parenting Behavior
Continuous or binary?	continuous	continuous	continuous	continuous

Level of significance (e.g., 0.05 percent)	0.05	0.05	0.05	0.05
Number of sides of test (one- or two-tailed)	One-tailed	One-tailed	One-tailed	One-tailed
Power (e.g., 80 percent)	80%	80%	80%	80%
Total number of individuals in analytic sample	620	620	620	620
If binary, enter mean of outcome variable				
If continuous outcome, enter the standard deviation of the outcome (>0)				
Proportion of individual-level (or within-group) variance explained by covariates				
For cluster RCTs: intraclass correlation coefficient	N/A	N/A	N/A	N/A
For cluster RCTs: proportion of group-level variance of	N/A	N/A	N/A	N/A

outcome explained by covariates				
Minimum detectable impact				
Minimum detectable effect size	0.2	0.2	0.2	0.2

If you did not provide report your assumptions using the table above, please enter them here.

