10. DATA COLLECTION

10.1. CONSTRUCTS AND MEASURES

Clearly articulate the constructs of interest, measures to evaluate those constructs, and specific data collection instruments. Provide any information on the reliability and validity of the data collection instruments. For standardized instruments, you may provide the citation for the instrument.

Measure	Sample	Variable Type	Data source(s)	Variable Name	Definition
Co-parenting relationship behaviors	Has at least one child age 24 or younger	Continuous (range from 1 to 5 where 1 is strongly disagree and 5 is strongly agree)	nFORM entrance, OLLE follow-up	Copar_Beh	Average of 11 survey items that relate to positive interactions with the mother of participant's youngest child
Parenting relationship behaviors	Has at least one child age 24 or younger, saw child within past month	Continuous (range from 1 to 5 where 1 is never and 5 is every day or almost every day)	nFORM entrance, OLLE follow-up	Par_Beh	Average of 10 to 11 survey items (depending on child age) that relate to frequency of positive interactions with participant's youngest child
Parenting relationship attitudes	Has at least one child age 24 or younger, saw child within past month	Continuous (range from 1 to 5 where 1 is always and 5 is never)	nFORM entrance, nFORM exit	Par_Att	Average of 6 survey items that relate to frequency of feelings about participant's youngest child
Parenting relationship behaviors	Has at least one child age 24 or	Continuous (range from 1 to 5 where 1 is	nFORM entrance, ,	Parent_Fight	Reported frequency of

	younger, saw child within past month	never and 5 is every day or almost every day)	OLLE follow-up		fighting with child
Partner relationship behaviors	All survey respondents	Continuous (range from 1 to 5 where 1 is never and 5 is always)	OLLE pre-survey, OLLE post-survey, OLLE follow-up	Partner_Fight	Reported frequency of fighting with partner
Partner relationship behaviors	All survey respondents	Continuous (range from 1 to 5 where 1 is never and 5 is always)	OLLE pre-survey, OLLE post-survey, OLLE follow-up	Partner_Disagree	Average of 7 survey items related to frequency of disagreement with partner on different topics

* you may add rows by hitting the tab button, or right click and select insert row below

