Steps begin by creating constructs that serve as the dependent variables used to model comparisons of primary outcomes—parent, co-parent, and partner relationship behaviors—and secondary outcomes—parenting attitudes. Constructs are comprised of the relevant survey items on the nFORM Community Fathers Survey and the OLLE Survey. Constructs are confirmed with psychometric evidence derived from confirmatory factor analysis (CFA), except when they are already supported by evidence of reliability and validity or based on one item that is sufficiently broad to investigate an outcome. Next, results from baseline equivalency analyses identify co-variates to specify in the model that control for any detected differences in participant characteristics or developmental starting points in healthy family relationships and economic stability. Model results are interpreted to determine if assignment to the treatment group positively predicts ($p < .05$) more improved outcomes than the control group 6-months after enrollment into TCD services for behavior outcomes and immediately following program completion for attitudinal outcomes.

Finally, type 1 and type 2 error are controlled in this study. Type I error is the rejection of a true null hypothesis (also known as a "false positive" finding or conclusion; example: "an innocent person is convicted"). We control for type 1 error in two ways. First, alpha levels are set at .05, so only 1 in 20 findings should result in a false positive, and we plan to use the Bonferroni correction method to adjust for multiple hypothesis tests. Second, research questions are limited to modeling six outcomes. Type II error is the non-rejection of a false null hypothesis (also known as a "false negative" finding or conclusion; example: "a guilty person is not convicted"). We control for Type 2 error by having sufficient power to detect small or nearly small minimum detectable effect sizes. (The estimated effect sizes are all almost small effects that would be detected, based on best practices outlined by Cohen (1988) of small effect sizes <0.02 and medium effect sizes <0.15 .)

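### The stated 80% power at an effect of 0.2 assumes no multiplicity correction; under the SAP's Bonferroni plan it is about 54% (six measures) or 60% (four questions) without covariate gain, and the divisor is not stated

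*SAP*

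**What the plan says.** **Power.** Protocol section 9.3 has four outcome columns: parenting attitudes, partner relationship behavior, parenting behavior and co-parenting behavior. Each column gives alpha 0.05, one-tailed, 80% power, 620 analysed and 0.2 in the row "Minimum detectable effect size". The row "Proportion of individual-level (or within-group) variance explained by covariates" is blank.

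**Multiplicity.** The SAP (section 1, Analytic approach) sets alpha at .05 and says "we plan to use the Bonferroni correction method to adjust for multiple hypothesis tests". As a second, separate safeguard it adds that "research questions are limited to modeling six outcomes". It then states: "We control for Type 2 error by having sufficient power to detect small or nearly small minimum detectable effect sizes". No corrected alpha appears, and no power at a corrected alpha.

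**Outcomes.** Protocol section 1.2 marks all four research questions, R1 to R4, as confirmatory. Protocol section 10.1 and the SAP's measure matrix list six measures. Partner relationship behaviors (question R2) has two: frequency of fighting with the partner, and "Average of 7 survey items related to frequency of disagreement with partner on different topics". Parenting behavior (question R3) also has two. Parenting attitudes (R1) and co-parenting (R4) have one each. R1 is confirmatory in section 1.2, with the outcome "Healthier parenting attitudes for the Treatment Group that receives enhanced services", but the SAP lists parenting attitudes as a secondary outcome.

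**Success rule.** The SAP twice states success as p < .05 and does not say whether that p-value is adjusted. It does not name the sidedness of the tests.

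**The concern.** Bonferroni divides alpha by the number of tests, and the power table uses the undivided 0.05. The stated power may therefore belong to an analysis that is not the one planned. If so, a reader of a null result would credit the trial with more ability to detect an effect of 0.2 than it has.

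The second problem is the threshold. The documents support at least three counts:

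- six measures (the SAP matrix and its sentence on six outcomes);
- four confirmatory questions (protocol sections 1.2 and 9.3);
- three primary behavior constructs (the SAP, which moves parenting attitudes to secondary).

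Nothing says whether R2 and R3 succeed on one of their two measures or need both. If this is left open, a confirmatory conclusion could depend on a choice made after the data are seen.

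**Working it through.** **Inputs.** 620 analysed, 310 per arm (protocol 9.2 and 9.3). Effect 0.2 in standard deviation units, one-tailed alpha 0.05, 80% power (9.3). R-squared, the share of outcome variance explained by covariates, is blank in 9.3. I take 0 as an assumption and vary it below.

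**Formulas** (normal approximation, equal arms, k = Bonferroni divisor):

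- SE = sqrt(4 × (1 − R-squared) / 620), which is 0.0803 at R-squared = 0
- power = Φ(0.2/SE − z), with z the upper 0.05/k point
- minimum detectable effect = (z + 0.8416) × SE

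**The plan's own figure** (k = 1): 0.2/0.0803 = 2.490, and 2.490 − 1.645 = 0.845, so power is 80.1%. The minimum detectable effect is (1.645 + 0.842) × 0.0803 = 0.1997. Both match the table, so it contains no correction and needs no covariate gain.

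**With Bonferroni, R-squared = 0:**

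| Family | k | alpha | z | Power at 0.2 | Minimum detectable effect |
|---|---|---|---|---|---|
| No correction | 1 | 0.05 | 1.645 | 80.1% | 0.200 |
| Within a two-measure construct only | 2 | 0.025 | 1.960 | 70.2% | 0.225 |
| Three primary constructs | 3 | 0.0167 | 2.128 | 64.1% | 0.239 |
| Four confirmatory questions | 4 | 0.0125 | 2.241 | 59.8% | 0.248 |
| Six measures | 6 | 0.0083 | 2.394 | 53.8% | 0.260 |

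With the noncentral t distribution the last two powers are 59.6% and 53.6%. These are powers per test.

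**Covariates.** For R-squared of 0.1, 0.3 and 0.5, power is 59.1%, 72.0% and 87.0% over six tests, and 64.9%, 76.9% and 90.0% over four. The R-squared that restores 80% at 0.2 is 1 − (0.2 / minimum detectable effect at R-squared = 0)²:

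- six tests: 1 − (0.2/0.260)² ≈ 0.41
- four tests: 1 − (0.2/0.248)² ≈ 0.35
- three tests: 1 − (0.2/0.239)² ≈ 0.30

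**Sidedness.** If the SAP's tests were two-sided, power at R-squared = 0 would be 70.2% uncorrected, 49.7% over four and 44.1% over six.

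**Effect on a conclusion.** An unadjusted one-tailed p of 0.010 is below 0.0167 and 0.0125 but above 0.0083. It succeeds with a divisor of three or four and fails with six.

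**The case against.** *Six is the natural divisor.* The sentence on six outcomes follows the Bonferroni sentence, and the matrix has six rows. That is a fair reading, but the SAP offers the six outcomes as a separate safeguard, and the protocol's confirmatory count is four. If six is meant, power is at the low end of the across-question range, 54%.

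*A rule of p < .05 is compatible with Bonferroni if the p-values are adjusted.* True. The SAP has only to say so.

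*The SAP itself never claims 80% at 0.2.* It claims power for small or nearly small effects, citing benchmarks of 0.02 and 0.15. If these are on the f-squared scale, an effect d of 0.2 is 0.2²/4 = 0.010 and 0.26 is 0.017, so that description can stand. The protocol's 80% at 0.2 cannot stand alongside the correction. The table is right for its own inputs; the error is that those inputs are not the planned test.

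*Covariates may restore the power.* This is the strongest point. Every measure has a baseline wave, the SAP speaks of greater improvements, and single-item outcomes require both surveys. A baseline-outcome correlation of about 0.64 would give R-squared of 0.41 (0.64² ≈ 0.41). But the SAP enters covariates only where a baseline difference is detected, so it does not guarantee that the baseline score is in the model. The 54% and 60% remain conditional on R-squared = 0.

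*The analysed number will not be 620 for every outcome.* Correct: the SAP expects it to vary, and three measures require having seen the child in the past month. Any outcome with fewer than 620 has lower power than shown.

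**Conclusion.** The concern holds. On the protocol's own inputs, 80% power at 0.2 belongs to an uncorrected one-tailed test. The planned correction gives 54% over six measures (minimum detectable effect 0.26), 60% over four questions (0.25) or 64% over three constructs (0.24). Correcting only within the two-measure constructs leaves 70% for those and 80% for the others. These figures assume 620 analysed, equal arms, one-tailed tests and no variance explained by covariates. They improve if covariates explain substantial variance and worsen if the tests are two-sided or fewer than 620 are analysed.

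Separately, the family, the divisor and the status of parenting attitudes are not fixed, and the choice can change a confirmatory conclusion. This must be corrected before analysis.

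**What to change.** 1. Name the confirmatory family and the Bonferroni divisor in the SAP. Give parenting attitudes the same status in both documents, and say whether questions R2 and R3 need one or both of their two measures.
2. State the SAP's success rule, in both places, as multiplicity-adjusted p < .05, and carry the protocol's one-tailed tests into the SAP explicitly.
3. Restate power or the minimum detectable effect at the corrected alpha, with the assumed R-squared and the analysed number for each outcome. At 620 and R-squared = 0, the minimum detectable effect is about 0.26 for six tests or 0.25 for four.

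Optional: use Holm's procedure, which has the same family-wise control and is never less powerful than Bonferroni; and name the scale of the 0.02 and 0.15 benchmarks.

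The cost is wording in the SAP and the power table, and a less favourable stated figure. No new participants or data are needed. Study enrollment was due to end on 11-30-2024 and the SAP is dated 12/9/2024, so the restated power informs interpretation, not sample size. Follow-up surveys were scheduled to 05/31/25, so on that timetable the family could still be fixed before all outcomes were in.

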9.2. IMPACT EVALUATION ONLY: SAMPLE SIZE

If an impact evaluation is proposed, state the intended sample size (overall and by year), estimated attrition, and the anticipated size of the analytic sample (for both program/treatment and control/comparison groups). If the estimated analytic sample is expected to vary by outcome measure (e.g., outcomes measured using administrative records vs. survey data), you may copy the table below and label accordingly.

Year	Estimated Sample Size (# of individuals randomly assigned)		Estimated Size of Analytic Sample (# of individuals at analysis)	
	Treatment	Comparison	Treatment	Comparison
Year 1	N/A	N/A	N/A	N/A
Year 2	70	70	49	49
Year 3	162	162	113	113
Year 4	162	162	113	113
Year 5	50	50	35	35
TOTAL	443	443	310	310

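### The planned Bonferroni correction is valid but needlessly conservative: Holm gives the same 0.05 family-wise guarantee and adds 0 to about 12 points of power per true effect

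*SAP*

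**What the plan says.** The SAP, under Analytic approach in section 1, describes two controls on false positives. The first is a 0.05 significance level, read as one false positive in twenty findings, to which a correction is added: "we plan to use the Bonferroni correction method to adjust for multiple hypothesis tests". The other control is a limit on the number of tests: "research questions are limited to modeling six outcomes".

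No step-down or hierarchical method is named, and no reason is given for the single-step form. The divisor is not stated. The same section still words success as p < .05 for each outcome measure, without saying whether p is adjusted. No confidence intervals are mentioned, so the decisions rest on p-values.

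The power table in protocol section 9.3 covers four confirmatory outcomes. Each is entered at "Level of significance (e.g., 0.05 percent) 0.05" and "Number of sides of test (one- or two-tailed) One-tailed".

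**The concern.** Bonferroni compares every p-value with 0.05/m, where m is the number of tests. Holm orders the p-values and compares the smallest with 0.05/m, the next with 0.05/(m-1), and so on, stopping at the first failure. The family-wise guarantee is the same and the thresholds are never stricter, so a plan that decides outcome by outcome on p-values has little reason to prefer the single-step form.

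This matters more when several effects are real at once, because each rejection loosens the next threshold. The protocol expects that situation: sections 3 and 4 predict better results in the treatment group on every outcome. Power is also short. The 80% in section 9.3 is calculated at an uncorrected 0.05, so any correction lowers it. At stake is whether real effects on some of the relationship outcomes go unconfirmed when an equally rigorous rule would have confirmed them.

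**Working it through.** **Inputs from the documents.** Analysed sample: "Total number of individuals in analytic sample 620", split 310 and 310 in protocol section 9.2. Effect size: 0.2 SD (section 9.3). Level: 0.05, one-tailed. Power: 80%. Number of tests: six by the SAP's count, or four by the protocol's confirmatory questions (section 1.2).

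**Assumptions.** SD = 1, because the effect is standardised and the SD entry is blank. No variance is explained by covariates (also blank). The correlation between outcomes is not given, so 0, 0.3 and 0.5 were tried, with 0.3 as the working value. Two-tailed tests were also run, because the SAP does not state the number of sides.

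**Step 1: reproduce the plan's figure.** The standard error of the standardised difference is sqrt(2/310) = 0.0803, so the expected z is 0.2/0.0803 = 2.49. One-tailed power at 0.05 is Phi(2.49 - 1.645) = 0.801. The minimum detectable effect is (1.645 + 0.842) x 0.0803 = 0.1997. The stated 0.2 at 80% is reproduced, without any correction.

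**Step 2: apply Bonferroni (one-tailed).**
- Six tests: 0.05/6 = 0.00833, critical z 2.394, power Phi(2.490 - 2.394) = 0.538. Minimum detectable effect at 80% power: (2.394 + 0.842) x 0.0803 = 0.260.
- Four tests: 0.05/4 = 0.0125, critical z 2.241, power Phi(2.490 - 2.241) = 0.598. Minimum detectable effect: 0.248.

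**Step 3: why Holm keeps the guarantee.** Suppose m0 of the m null hypotheses are true. When Holm makes its first false rejection, all m0 true nulls are still in play, so the threshold is at most 0.05/m0. The chance that any of m0 true-null p-values falls below 0.05/m0 is at most 0.05, whatever their dependence. Holm's six thresholds are 0.0083, 0.0100, 0.0125, 0.0167, 0.0250 and 0.0500. None is below Bonferroni's 0.0083, so every Bonferroni rejection is also a Holm rejection.

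**Step 4: size of the gain.** Equicorrelated normal test statistics were simulated, 400,000 draws per scenario, with both rules applied to the same draws. Results for 310 per arm, 0.2 SD and correlation 0.3:

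| Tests | Truly affected | Sides | Average power per true effect, Bonferroni to Holm | Chance of any false rejection, Bonferroni to Holm |
|---|---|---|---|---|
| 6 | 1 | one | 54% to 54% | 3.8% to 4.3% |
| 6 | 3 | one | 54% to 57% | 2.4% to 4.1% |
| 6 | 6 | one | 54% to 65-66% | none possible |
| 6 | 6 | two | 44% to 53% | none possible |
| 4 | 2 | one | 60% to 62% | 2.4% to 4.3% |
| 4 | 4 | one | 60% to 70% | none possible |
| 4 | 4 | two | 50% to 58-59% | none possible |

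Further results:
- Correlations of 0 and 0.5 (one-tailed, all affected) give Holm power of 65-66% for six tests and 70-71% for four.
- The chance of at least one true finding, six affected, is 93.7% under both rules. The chance of confirming all six rises from 10% to 35%.
- If all six true effects are 0.1 SD, one-tailed power rises only from about 12.5% to 14.6%.
- Bonferroni never rejected a hypothesis that Holm kept, and Holm's family-wise error stayed at or below 0.05 throughout.

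**The case against.** **Bonferroni is valid.** It is a common, prespecified and conservative choice. Nothing in the documents contradicts it, and no conclusion reached with it would be wrong. This stands.

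**The extra power is not entirely free.** A reader might infer that Holm leaves the actual false-rejection rate where it was. It does not: with half the outcomes null the rate rises from 2.4% to 4.1-4.3%. Holm uses error that Bonferroni leaves unspent, though it remains inside the 5% the plan allows. Holm also has no equally simple set of simultaneous confidence intervals. The SAP plans none, so this costs little here.

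**The larger gains are a best case.** A reader might take 8 to 13 points as the general benefit. That range needs every outcome to have a true effect of 0.2 SD with the full 310 per arm. A shared predicted direction does not show that all effects are real. The SAP also restricts three of the six measures to fathers who saw the child within the past month and expects samples to vary with missing data, so a uniform 310 is optimistic.

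**The benefit depends on a family the documents do not define.** There are six measures but four confirmatory questions, and parenting attitudes are confirmatory in protocol section 1.2 yet secondary in the SAP. If correction were made within each research question, R1 and R4 have one measure each and gain nothing. R2 and R3 have two each and gain about 6 points if both effects are real, and about nothing if one is. That Holm rejects at least as much holds for any family; the size of the gain does not.

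**The timing is late.** The SAP is dated 12/9/2024, after the listed end of impact-study enrolment (11-30-2024) and the planned end of exit surveys (08/01/24). A less strict decision rule adopted at this stage needs a dated justification. This stands and is carried into the fix.

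**Conclusion.** The point holds as an avoidable inefficiency. For the same tests and the same 0.05 guarantee, Holm is never less powerful than the planned correction, and the plan uses nothing that would be lost by switching. The gain in average power per true effect over six one-tailed tests runs from almost nothing to about 12 points, depending mainly on how many effects are real and how large they are. It rests on 310 per arm, an effect of 0.2 SD and an assumed correlation of 0.3; the two other correlations tried change it little.

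Two stronger readings are not supported. One is that the SAP contains an error here. It does not, because Bonferroni controls family-wise error. The other is that Holm repairs the study's power. Average power with all outcomes affected reaches at most about 66% with six tests and 71% with four, not 80%. The uncorrected level in protocol section 9.3 and the undefined family are separate problems that remain under either method.

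**What to change.** In the SAP's Analytic approach:
1. Replace the Bonferroni correction with the Holm step-down procedure at family-wise 0.05.
2. List the outcome measures in the family explicitly and state the number of sides. Either method needs this.
3. Report Holm-adjusted p-values, and state that each p < .05 criterion in the section applies to them.
4. Date the change, and record that it was made before any comparison of outcomes by study group.

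The cost is a few lines of SAP text and no new data. The trade-offs are the loss of simple matching simultaneous intervals and the use of error that Bonferroni leaves unspent. If simultaneous intervals are wanted, Bonferroni-width intervals can still be shown alongside. The power statement should be corrected separately, since this change does not bring it back to 80%.
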